4.1.3 Missing Data

In general, missing data will not be imputed unless methods for handling missing data are specified.

4.2 Protocol Deviations

- The protocol deviations are reviewed and categorized as significant and non-significant prior to the database lock.
 - Significant protocol deviation: a protocol deviation that affects primary efficacy and safety assessments (as applicable), the safety or mental integrity of a subject, or the scientific value of the project.

- Non-significant protocol deviation: a protocol deviation that is identified but does not impact the endpoints (as applicable), the safety or mental integrity of a subject, or the scientific value of the project.

All the protocol deviations will be listed. The number and percentage of participants with significant protocol deviations by deviation reason (e.g., nonadherence to study drug, violation of select inclusion/exclusion criteria) will be summarized.

A by-participant listing will be provided for those participants who did not meet at least one eligibility (inclusion or exclusion) criterion. The listing will present the eligibility criterion (or criteria if more than one deviation) that participants did not meet and related comments, if collected.

4.3 Statistical Hypotheses

The statistical hypotheses are as follows:

- Null hypothesis (H_0): difference in proportion of CRR responders (daxdilimab vs placebo) = 0
- Alternative hypothesis (H_a): difference in proportion of CRR responders (daxdilimab vs placebo) $\neq 0$

4.4 Analysis Sets

4.4.1 Full Analysis Set

The Full Analysis Set will include all randomized participants who receive any dose of trial intervention in the study. Participants will be analyzed according to the treatment randomized. The efficacy analysis will be based on the Full Analysis Set.

4.4.2 Safety Analysis Set

Safety Analysis Set will include all participants who receive any dose of trial intervention in the study. Participants will be analyzed according to the treatment that they actually received. Safety, PD, and ADA analyses will be based on the Safety Analysis Set.

4.4.3 Pharmacokinetic (PK) Analysis Set

The PK Analysis Set will include all participants who receive any dose of daxdilimab in the study and have at least one quantifiable serum PK observation post first dose. Participants will be analyzed according to the treatment that they actually received. The PK analysis will be based on the PK Analysis Set

4.4.4 Stage II Analysis Set

The stage II analysis set includes all participants who received at least one dose of trial intervention during the Stage II treatment period starting from [REDACTED].

4.4.5 Any Daxdilimab Set

The any daxdilimab analysis set includes all participants who receive at least one dose of daxdilimab during the trial.

4.5 Participant Disposition

A summary of participant disposition will be presented into two sections:

- Stage I
- Stage II

In Stage I section, the participants will be presented using the categories presented below.

- Screened
- Screen failed with reasons
- Randomized
- Randomized but not treated
- Randomized and treated
- Completed Stage I treatment
- Discontinued Stage I treatment with reasons
- Completed Stage I trial
- Discontinued Stage I trial with reasons

In Stage II section, the participants be presented using the categories presented below.

- Participants entered into Stage II trial
- Completed Stage II treatment
- Discontinued Stage II treatment with reasons
- Completed Stage II trial
- Discontinued Stage II trial with reasons

4.6 Trial Intervention Exposure

- The number of doses received, amount of the trial intervention received, total number of doses planned per protocol, durations of the trial intervention exposure, and treatment compliance will be summarized by treatment groups. For treatment compliance, the number and proportion of patients who had treatment compliance percentage in range by increments of 10% (i.e., $\geq 90\%$ to $\leq 100\%$; $\geq 80\%$ to $< 90\%$; $\geq 70\%$ to $< 80\%$ etc.) during treatment period will also be summarized by treatment groups. The summary will be produced using the Full Analysis Set for Stage I, Stage II and overall study. Duration of the trial intervention exposure is defined as follows:

- Stage I: [REDACTED] dose date – first dose date
- Stage II: last dose date + 28 – [REDACTED] dose date + 1

- The amount of trial intervention exposure: if a participant received a partial dose at a dosing visit, then the amount of trial intervention at that dosing visit will be estimated based on the actual volume administered.
- Treatment compliance for an individual participant = [Total number of doses received]/[Total number of doses planned per protocol] $\times 100\%$.

In addition, the total number of participants with missed doses and reasons for missed dose will be summarized by randomized treatment group and overall.

4.7 Demographics, Baseline Characteristics, and Medical History

The demographics (age, gender, race, ethnicity, height, weight, and body mass index) will be summarized by randomized treatment group and overall using the Full Analysis Set. Participant listings of these data will also be provided.

A summary of baseline disease characteristics, by randomized treatment group and overall, for the Full Analysis Set will include:

- Time from first diagnosis of proliferative LN based on a renal biopsy at baseline (baseline renal biopsy may be obtained within 6 months prior to signing the informed consent form (ICF) or during the Screening Period)
- Pre-randomization urine protein to creatinine ratio (UPCR) ($< 3.0 \text{ mg/mg}$ vs $\geq 3.0 \text{ mg/mg}$) (if more than one UPCR measurements available, use the last valid measurement),
- Screening estimated glomerular filtration rate (eGFR) ($< 60 \text{ mL/min/1.73m}^2$ vs $\geq 60 \text{ mL/min/1.73m}^2$),
- eGFR (calculated by the MDRD formula),
- 24-hour UPCR,
- Renal-biopsy lupus nephritis class (Class III (\pm class V) vs class IV (\pm class V)),
■ [REDACTED]
■ [REDACTED]
- The Systemic Lupus International Collaborating Clinics/American College of Rheumatology Damage Index (SDI),
■ [REDACTED]
■ [REDACTED]
- Baseline OCS use (yes vs. no),
- Baseline OCS dose ($\leq 7.5 \text{ mg/day}$ vs $> 7.5 \text{ mg/day}$),
- Baseline MMF/MPA use (yes vs. no),
- Baseline MMF/MPA dose ($\leq 2 \text{ gm/day}$ vs $> 2 \text{ gm/day}$),
■ [REDACTED]

- Antinuclear antibodies (ANA) $\geq 1:80$ (yes vs. no),

- [REDACTED]
- [REDACTED]
- [REDACTED]

Significant medical history findings will be summarized by system organ class (SOC) and preferred term (PT) using Medical Dictionary for Regulatory Activities (MedDRA) (Version 23 or later), by randomized treatment group and overall.

4.8 Efficacy Analyses

4.8.1 Primary Efficacy Endpoint and Analysis

4.8.1.1 Primary Efficacy Endpoint and Estimand

The estimand of primary interest is defined as follows, using composite variable strategy to address intercurrent events: participants for receipt of rescue therapy or treatment discontinuation will be treated as failure to meet CRR and considered as non-responder. For participants who experience multiple intercurrent events, data will be handled according to the first intercurrent event.

1. Population: Participants in the Full Analysis Set
2. Variable (endpoint measure): CRR at Week 48 and sustained through Week 52. CRR is defined by meeting all of the following criteria:
 - i. eGFR ≥ 60 mL/min/1.73m² or no worse than 15% below baseline.
 - ii. 24-hour UPCR ≤ 0.5 mg/mg.
 - iii. No use of restricted medication beyond the protocol allowed threshold before assessment.
 - iv. No discontinuation of study intervention
3. Intercurrent event:
 - a. Rescue medications: Captured in the primary variable definition.
 - b. Treatment discontinuation: Captured in the primary variable definition.
4. Population-level summary: Difference in proportions of responders between the daxdilimab group and placebo group (daxdilimab [REDACTED] mg or [REDACTED] mg vs. placebo)

4.8.1.2 Primary Efficacy Analysis

The proportion of participants achieving CRR at Week 48 and sustained through Week 52 in the daxdilimab group will be compared to that of the placebo group using a logistic regression model with treatment, adjusting for baseline eGFR value and baseline 24-hour UPCR value in the model using the full analysis set. The baseline 24-hour UPCR will be derived using the urine sample collected at Week 0 (Day 1) prior to randomization and administration of first dose of study intervention. Baseline eGFR will be based on the measurement available prior to the first dose of study intervention. The

difference in proportions of responders of daxdilimab vs placebo will be estimated together with its associated 2-sided 90% confidence interval (CI). Longitudinal presentations of results over time up to [REDACTED] based on the same analysis will be created. A bar chart will also be provided showing the proportion of participants meeting the criteria for CRR and individual components of CRR at Week 48 and maintained through Week 52 by treatment groups. A line plot over time will also be produced by treatment groups.

4.8.1.3 Subgroup analyses of primary endpoint

The following subgroups will be investigated for the primary endpoint:

- Renal-biopsy lupus nephritis class -- the World Health Organization (WHO) or 2003 ISN/RPS classification (Class III (\pm class V) vs. class IV (\pm class V))
- Gender (male vs. female)
- Race (white, black or African American, and other)
- Ethnicity (Hispanic/Latino vs. not Hispanic/Latino)
- Baseline IFN gene signature (high vs. low)
- Age group (<65 vs. \geq 65)
- Region (North America + Western Europe vs. rest of the world)
- ADA positive at any time (yes vs. no)
- Pre-randomization urine protein to creatinine ratio (UPCR) (< 3.0 mg/mg vs. \geq 3.0 mg/mg)
- Screening estimated glomerular filtration rate (eGFR) (< 60 mL/min/1.73m² vs. \geq 60 mL/min/1.73m²)

The nominal p-value and 90% CIs of treatment effect will be provided for each subgroup analysis. Given that the number of participants in some subgroups may be limited, subgroup categories may be combined as appropriate. Otherwise, the subgroup analysis may not be performed if deemed infeasible based on sample size.

Forest plots will be generated to visually present the consistency of treatment effect in different subgroups with overall treatment effect. Other subgroup analyses may be explored as needed.

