Study HZN7734.P1b.S1 evaluated the PK, PD, and safety of 3 monthly doses of daxdilimab. The study enrolled 31 subjects with SLE, cutaneous lupus erythematosus (CLE), Sjogren's syndrome, systemic sclerosis, PM, or DM. Subjects received placebo or daxdilimab at 5, 50, and 150 mg by SC injection. Daxdilimab PK exposure was approximately dose proportional over the dose range investigated. Apparent steady-state clearance (CLss/F) values were similar across dose groups and ranged from 0.62 to 1.18 L/day. The $t_{1/2}$ was 14.6 days for subjects receiving 150 mg daxdilimab. Sixteen of 22 (72.7%) daxdilimab-treated subjects and 6 of 9 (66.7%) placebo treated subjects experienced at least one TEAE. There were no deaths in the trial. One placebo-treated subject and no daxdilimab-treated subjects experienced treatment emergent SAEs. No subject experienced an AE leading to treatment discontinuation. No treatment-emergent ADA was observed in subjects treated with daxdilimab. In subjects with CLE, Cutaneous Lupus Erythematosus Disease Area and Severity Index-Activity (CLASI-A) scores improved more in the daxdilimab 150 mg group than the placebo group. After 3 monthly SC doses of daxdilimab 50 mg or 150 mg, the median change in percent pDCs at Day 85 was -54.1% in the daxdilimab group, compared to a +9.8% in the placebo group.

To date, no adverse drug reactions (ADRs) for daxdilimab have been identified. Important potential risks for daxdilimab include viral infection and viral reactivation, opportunistic infection, malignancy (other than non-melanoma skin cancer), and hypersensitivity reactions including anaphylaxis. Other potential risks include injection site reactions, vaccine interaction, drug-drug interactions, and reproductive toxicity.

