4.13 Immunogenicity

The ADA status will be summarized by the categories defined in [Table 6](#). The ADA incidence rate may also be summarized by treatment group at each time point, where the incidence is the proportion of the participants with ADA positive results post-baseline only or boosted their pre-existing ADA during the study period. The cutoff for the

[figure not shown]
boosted ADA will be determined before the database lock for the primary analysis. The impact of ADA on PK will be assessed. If data allow, any confirmed ADA positive samples will be tested for ADA titer and the presence of neutralizing antibodies to daxdilimab. The number and percentage of participants who develop positive ADA will be summarized by randomized treatment group, and the impact of ADA on efficacy and safety will be evaluated.

[figure not shown]
The ADA summary will be produced for Stage I using Safety Analysis Set and for the overall study using Any Daxdilimab Analysis Set. For the overall study summary, the baseline positive is defined as any positive ADA prior to the first administration of daxdilimab.

Table 6 Definition of ADA Status

ADA Status	Definition
Prevalence (Positive during the study)	ADA positive observed at least once during the study (baseline included)
Negative during the study	ADA positive not observed at any visit during the study (baseline included)
Baseline positive	ADA positive observed at baseline regardless of the post-baseline ADA status
Post-baseline positive	ADA positive observed at least once during post-baseline regardless of the baseline ADA status
Only baseline positive	ADA positive observed at baseline but not observed at any time post-baseline
Only post-baseline positive (treatment-induced)	ADA positive not observed at baseline but observed at least once post-baseline
Both baseline and post-baseline positive	ADA positive observed at baseline and observed at least once post-baseline
Persistent positive	Treatment-induced ADA positive at ≥ 2 post-baseline assessments (with ≥ 16 weeks between first and last positive) or positive at the last post-baseline assessment
Transient positive	Treatment-induced ADA post-baseline positive but does not fulfil the criteria of persistent positive

ADA = anti-drug antibodies.

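### The planned ADA subgroup of the primary endpoint splits the arms on a variable largely set after randomisation by exposure to daxdilimab, so neither row is a randomised comparison with placebo

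*SAP*

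**What the plan says.** SAP 4.8.1.3 names ten subgroup factors for the primary endpoint. Nine are fixed before treatment: biopsy class, sex, race, ethnicity, baseline IFN signature, age, region, pre-randomisation UPCR and screening eGFR. The tenth is "ADA positive at any time (yes vs. no"). All ten get the same output: "The nominal p-value and 90% CIs of treatment effect will be provided for each subgroup analysis", and "Forest plots will be generated to visually present the consistency of treatment effect in different subgroups with overall treatment effect". A small-numbers clause lets categories be combined and adds that "the subgroup analysis may not be performed if deemed infeasible based on sample size". For the ADA factor the section states no time window, no restriction to the daxdilimab arms and no caution that it arises after randomisation.

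SAP 4.13, Table 6, has the nearest definition of the factor, positive during the study: "ADA positive observed at least once during the study (baseline included"). Treatment-induced ADA is separate: "ADA positive not observed at baseline but observed at least once post-baseline". The same section says that "the impact of ADA on efficacy and safety will be evaluated", without giving a method. Protocol 8.8 says only that an association with safety and efficacy may be explored if the data permit.

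Protocol 6.2.1 gives the placebo as normal saline. On the likely ADA rate, Protocol 2.2.1 reports no ADA in the single-dose study and, for the multiple-dose study, "No treatment-emergent ADA was observed in subjects treated with daxdilimab".

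**The concern.** A subgroup effect is a randomised comparison when membership is fixed before treatment, or at least cannot be altered by it. Treatment-induced ADA fails that test because it needs exposure to daxdilimab.

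- **Positive row.** Daxdilimab participants would be mainly those in whom the drug induced antibodies. Any placebo participants would be there through pre-existing or non-specific reactivity. These are different kinds of participant, and the placebo side may be empty.
- **Negative row.** The placebo side is almost the whole arm. The daxdilimab side has lost those who formed antibodies, and their counterparts in the placebo arm cannot be identified and removed. If people prone to form ADA differ in prognosis, the contrast mixes drug effect with selection.

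At stake is how the result is read. The row would sit beside nine pre-treatment factors on a plot meant to show consistency of effect, with its own p-value and interval.

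**Working it through.** **Inputs from the documents.** 70 per arm, placebo response 25%, target 45%, two-sided alpha 0.10 (SAP 2.3). No ADA rate is given for this trial. The induced ADA rate r, the pre-existing positivity b and the response q in ADA-positive daxdilimab participants are therefore assumptions, shown over a range.

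**1. The plan's own figure.** With pooled rate 0.35:

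[0.20 x sqrt(70) - 1.645 x sqrt(2 x 0.35 x 0.65)] / sqrt(0.25 x 0.75 + 0.45 x 0.55) = (1.673 - 1.110) / 0.660 = 0.855

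This gives power 0.804, which reproduces the stated 80%. Nothing below alters it.

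**2. Size of the positive row in Stage I.** Expected placebo positives are 70 x b: 0 at b = 0, 1.4 at 2%, 3.5 at 5%. At 2% the chance of none is 0.98^70 = 0.24. With b = 0, expected daxdilimab positives per arm are 70 x r: 1.4 at 2%, 7 at 10%, 14 at 20%, 21 at 30%. With 14 against 2 participants and rates of 45% and 25%, the 90% CI half-width is

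1.645 x sqrt(0.45 x 0.55/14 + 0.25 x 0.75/2) = 0.55

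or 55 points, with power of about 11%.

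**3. Bias in the negative row.** Let p be the response in the whole daxdilimab arm. Since p = r x q + (1 - r) x p_neg,

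p_neg = (p - r x q) / (1 - r)

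To isolate bias, take a drug that does nothing, so p = 25% and placebo is 25% (b = 0). Any non-zero difference is then selection alone.

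| ADA rate r | q = 10% | q = 25% | q = 45% |
|---|---|---|---|
| 2% | +0.3 | 0 | -0.4 |
| 10% | +1.7 | 0 | -2.2 |
| 20% | +3.8 | 0 | -5.0 |
| 30% | +6.4 | 0 | -8.6 |

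Entries are points, p_neg minus 25%. For example, at r = 20% and q = 10%, (0.25 - 0.02)/0.80 = 28.75%. At q = 45%, (0.25 - 0.09)/0.80 = 20.0%. The bias vanishes only when ADA formation is unrelated to response (q = 25%).

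For scale, the 90% CI half-width of the first example, with 56 against 70 participants, is 1.645 x sqrt(0.2875 x 0.7125/56 + 0.25 x 0.75/70) = 13.1 points.

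**4. Why the time window matters.** SAP 4.15 reruns all primary analyses at the final analysis, and by then placebo participants without a partial or complete response have been given daxdilimab. SAP 4.1 limits the primary efficacy data to a visit that is redacted, but 4.8.1.3 does not say whether later ADA counts towards membership. If it did, newly positive placebo participants would all be primary-endpoint failures. Assume 40% of placebo reach at least a partial response and 10% of the switchers become positive. Then 70 x 0.60 = 42 switch and 4.2 are positive, with a complete response rate of 0%. A drug with no effect (25% among ADA-positive daxdilimab participants) would show +25 points in the positive row if these were its only placebo members.

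**The case against.** Four replies have force, and each limits what can be claimed.

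- **A shifted effect is not the same as bias.** A reader might infer that the negative row must inflate efficacy. Suppose the true rates are 45% and 25%, and ADA-positive participants respond at 25%. The negative row then shows (0.45 - 0.10 x 0.25)/0.90 = 47.2% at a 10% ADA rate and (0.45 - 0.20 x 0.25)/0.80 = 50.0% at 20%, against 25%. If untreated response is 25% whether or not someone would form ADA, these are correct effects for people who stay negative. Bias needs ADA formation to be related to prognosis, and the documents do not show that it is.
- **Placebo positives are possible.** A reader might infer that no placebo participant can be in the positive row. Table 6 counts baseline positives and ADA is sampled on Day 1, so a few can.
- **ADA may be rare.** The earlier studies found no treatment-emergent ADA. None in the 22 daxdilimab-treated subjects of the multiple-dose study gives a one-sided 95% upper limit of 1 - 0.05^(1/22) = 12.7%, after only three monthly doses. A higher rate under longer dosing is possible, but the range should start near zero.
- **The analysis is exploratory and may be dropped.** The p-values are nominal, and the small-numbers clause can remove the whole ADA analysis. A reader might infer that it would remove only the positive row, but its wording does not say so. The clause is discretionary, though, and rests on sample size. It does not address selection after randomisation, and it is least likely to apply when ADA is common, where the bias can be largest.

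**Conclusion.** The point stands as a defect of an exploratory analysis. The SAP plans a placebo comparison within strata defined largely by a consequence of daxdilimab exposure, and neither row is a randomised comparison. In Stage I the positive row would hold about 0 to 3.5 placebo participants, assuming 0% to 5% pre-existing positivity, and would carry almost no information. The negative row is biased if ADA formation is related to prognosis, in a direction that cannot be known beforehand. Under a drug with no effect, the bias is below 1 point at a 2% ADA rate and about +4 or -5 points at 20%, for response of 10% or 45% in ADA-positive participants. Those rates are illustrative, and the 20% shifts are small beside an interval half-width of about 13 points.

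The primary test, the fixed-sequence control of type I error and the sample size are unaffected. The documents do not support saying that efficacy will be overstated, or by how much.

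**What to change.** - Delete the ADA line from SAP 4.8.1.3 and from the forest plot.
- In SAP 4.13, specify a descriptive summary of complete renal response by ADA status within the daxdilimab arms, with no contrast against placebo. Count ADA only up to the Week 52 assessment, and keep that window when the analyses are rerun under 4.15.
- If a between-arm ADA subgroup is wanted, define it by baseline (Day 1) ADA status only. The schedule already includes that sample.

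The cost is one deletion and one short addition. The addition is needed because 4.13 now promises an evaluation of impact on efficacy without saying how. No power is lost, and no data beyond those already scheduled are needed.

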4.8.1.4 Control of Type I Error

1. The type I error rate will be controlled at a 0.1 level (2-sided) for the primary efficacy analysis using a fixed sequence testing procedure. The primary endpoint will be tested for daxdilimab [REDACTED] mg compared with placebo.
2. If p-value is \leq 0.1 in step 1, the primary endpoint will be tested for daxdilimab [REDACTED] mg compared with placebo. If step 1 test is not significant, the test for Daxdilimab [REDACTED] mg will not be performed.

4.8.1.5 Sensitivity Analysis

Race and ISN/RPS lupus nephritis disease class have been shown to be associated with poor prognosis and responses to treatment in patients with LN. A sensitivity analysis for

the primary endpoint with race and ISN/RPS classification included as additional covariates in the logistic regression model as defined in 4.8.1.2 will be performed to adjust the potential imbalance across treatment groups.

